6.2.2. Number of patients by complication symptom (Table 1.03x)

Analyzed:	Safety analysis set, efficacy analysis set
Analysis details:	
The number of patients with complications (number of patients with complications) and the proportion of patients with complications will be calculated for each SOC and PT by category of complications.
 
As for the order of output, data will be output in the descending order of the number of subjects for safety SOC, in the descending order of international consensus for SOC, in the descending order of the number of subjects for PT, and in the order of PT code.
 
The denominator of the proportions of patients with each complication will be the respective number of patients analyzed. For the safety analysis set, the number of patients with adverse reactions and the incidence of adverse reactions will be calculated, and for the efficacy analysis set, the number of patients with response and the incidence of response will be calculated.
 
The SELENA SLEDAI score will be used for the number of responders and response rate.
 
The denominator for the incidence of adverse reactions and response rate is the number of patients for each SOC and PT.

Complication	• Hepatitis B (Table 1.031)
Category	• Renal impairment (Table 1.032)

- Hepatic impairment (Table 1.033)
- Allergies (Table 1.034)
- Other (Table 1.035)

6.2.3. Number of patients by prior medication (anti-SLE drug) (Table 1.04x, 1.041x)

Analyzed:	Safety analysis set, efficacy analysis set
Analysis details:	
The number of target patients (number of patients using the drug) and use rate will be calculated by drug class, drug code (GSKdrug), and generic name, and output in the descending order of the number of patients in the safety analysis set and in the order of drug codes.
 
For the safety analysis set, the number of patients with adverse reactions and the incidence of adverse reactions (Table 1.041), adverse events (Table 1.042), and serious infections (Table 1.043) will be calculated, and for the efficacy analysis set, the number of responders and the response rate will be calculated.
 
For adverse drug reactions (Table 1.041) by prior treatment (anti-SLE drugs), similar analyses will be performed for each initial route of administration (IV, SC) (safety analysis set).
 
The SELENA SLEDAI score will be used for the number of responders and response rate.
 
The denominator of the usage rate is the number of patients in each analysis set.
 
The denominator for the incidence of adverse reactions and response rate is the number of patients per drug.

6.2.4. Number of patients by concomitant drug (anti-SLE drug) (Tables 1.05 and 1.051)

Analyzed:	Safety analysis set, efficacy analysis set
Analysis details:	
The number of target patients (number of patients using concomitant drugs) and use rate will be calculated by drug class, drug code (GSKdrug), and generic name, and output in the descending order of the number of patients in the safety analysis set and in the order of drug codes.
 
The number of patients with adverse reactions and the incidence of adverse reactions will be calculated for the safety analysis set, and the number of patients with response and the incidence of response will be calculated for the efficacy analysis set.
 
The same should be done for concomitant medications (anti-SLE drugs) used until Week 24 (described in Separate Volume 1).
 
The SELENA SLEDAI score will be used for the number of responders and response rate.
 
The denominator of the usage rate is the number of patients in each analysis set.
 
The denominator for the incidence of adverse reactions and response rate is the number of patients per drug.

6.2.5. Composition ratio of this drug administration status (Table 1.06x, 1.062x)

Analyzed:	Safety analysis set, efficacy analysis set
Analysis details:	
The number and composition ratio (%) and/or summary statistics will be calculated for each analysis set of route of administration, total number of doses, duration of treatment, total dose, and mean dose per administration.
 
For the status of administration of this drug (summary statistics), similar analyses will be performed by initial route of administration (IV, SC) (safety analysis set).
 
Unless otherwise specified, the denominator for the composition ratio (%) will be the total of each analysis set.

For total number of doses (IV), total dose (IV) [mg/kg], and average dose per administration (IV) [mg/kg], the denominator will be the number of subjects dosed by route (IV).

For total number of doses (SC), total dose (SC) [mg], and average dose per administration (SC) [mg], the denominator will be the number of subjects dosed by route of administration (SC).

Items:

- Primary route of administration (IV, SC SC is separated from AI and PFS and unknown)
- Route of administration (IV, SC, change *) *: Number of subjects for IV and SC excluding changes
- Duration of treatment (days) (<28, 28 ≤ to <168, 168 ≤ to <364, 364 ≤, unknown)
- Total number of infusions (IV) (<6, 6 ≤ to <11, 11 ≤ to <15, 15 ≤, unknown)
- Total number of SC injections (<13, 13 ≤ to <25, 25 ≤ to <37, 37 ≤ to <52, 52 ≤, unknown)
- Total dose (IV) [mg/kg] (≤ 50, 50 < to ≤ 100, 100 < to ≤ 140, 140 <, unknown)
- Total dose (SC) [mg] (≤ 2400, 2400 < to ≤ 4800, 4800 < to ≤ 7200, 7200 < to ≤ 10200, 10200 <)
- Mean single dose (IV) [mg/kg] (<10, 10, 10 <, unknown)
- Mean dose per administration (SC) [mg] (<200, 200, 200 <, unknown)

6.2.6. Duration of this drug treatment by reason for treatment discontinuation/completion 1.07 (Figure 1.02, 1.021)

Analyzed:	Safety analysis population
Analysis details:	According to "4.18 Handling of treatment continuation/discontinuation/completion," the data will be output by the number of patients with treatment discontinuation/completion, the reason for treatment discontinuation/completion, and the duration (weeks) of treatment with this drug until discontinuation/completion for the patients who discontinued/completed the treatment with this drug. Reasons for discontinuation/completion will be regarded as overlapping. A Kaplan-Meier plot (discontinuation rate) of time to discontinuation of this drug will be generated. In addition, a Kaplan-Meier plot of the extension period of this drug (continuation rate) will be provided.
Duration (weeks) of administration of this drug until discontinuation/completion of administration:	
 • <2, 2 ≤ to <4, 4 ≤ to <8, 8 ≤ to <12, 12 ≤ to <16, 16 ≤ to <20, 20 ≤ to <24, 24 ≤ to <28, 28 ≤ to <36, 36 ≤ to <44, 44 ≤ to <52, 52 ≤, unknown

6.3. SAFETY EVALUATION

6.3.1. List of occurrence of ADRs by patient background (Table 2.01)

Analyzed:	Safety analysis population
Analysis details:	
The number of target patients, the number of patients with adverse reactions, and the incidence of adverse reactions will be calculated for each patient background item.
 
The denominator of the incidence of adverse reactions is the number of patients included in each background item.

Patient characteristics:	
The following will be added to the section of "Patient composition ratio."
 
 • SELENA SLEDAI (baseline): ≤ 9, 10 ≤, unknown • PGA score (baseline): (0 ≤ to ≤ 1, 1 < to ≤ 2.5, 2.5 < to ≤ 3, unknown) • Anti-dsDNA antibody (baseline) [IU/mL]: <30, 30 ≤ • Complement Levels: 
 Low C3 and/or Low C4 Other than the above Unknown • C3 (baseline) [mg/dL]: (<90, 90 ≤, unknown) • C4 (baseline) [mg/dL]: (<10, 10 ≤, unknown)

6.3.2. Time to onset of adverse reaction/event (Tables 2.021~2.024, 2.061~2.065, Figure 2.01~2.05)

Analyzed: Safety analysis population, safety analysis population (patients for whom follow-up survey forms were collected)

Analysis details: The proportion of each SOC and PT will be tabulated by category of number of days to onset of adverse reaction/adverse event for each PT (weeks). In addition, the incidence of adverse reactions/adverse events and the cumulative incidence of adverse reactions/adverse events will be tabulated for all subjects and serious adverse reactions/adverse events.

The proportion will be presented by number of days as the sum of cases excluding overlapping adverse reactions/adverse events.

The cumulative percentage of cases by number of days will be presented. However, each case counts only in days for its first occurrence (first reaction/AE). "Unknown" in the same case shall be counted preferentially.

As for the order of output, data will be output in the descending order of the number of subjects by SOC in the total column, in the descending order of the number of subjects by PT, and in the order of PT codes.

Also, For the incidence of adverse events/serious adverse events (number of events/number of patients), a bar graph will be prepared for each category of time to onset (weeks). Similar bars will be produced for Hypersensitivity, Hypersensitivity "Infections (Including tuberculosis, pneumonia, pneumocystis pneumonia, sepsis, and opportunistic infection)," Hypersensitivity "Depression, suicidal ideation, suicide attempt" and Malignancy. However, "Depression, suicidal ideation, suicide attempt" and "malignant tumors" are handled as adverse events only.

The number of days with onset is calculated as follows.

Date of onset - date of start of treatment +1 (7 days is counted as 1 week)

*SOC and PT are summarized by SOC and PT, respectively, of initial onset.

*This should be done in the same way for events collected as follow-up (Table 2.061-2.065).

Time (weeks) to onset of adverse reaction/adverse event category: • <2, 2 ≤ to <4, 4 ≤ to <8, 8 ≤ to <12, 12 ≤ to <16, 16 ≤ to <20, 20 ≤ to <24, 24 ≤ to <28, 28 ≤ to <36, 36 ≤ to <44, 44 ≤ to <52, 52 ≤, unknown

event category:

Category of time (weeks) to onset of event to be collected • <52, 52 ≤ to <60, 60 ≤ to <68, 68 ≤ to <76, 76 ≤ to <84, 84 ≤ to <92, 92 ≤ to <100, 100 ≤ to <108, 108 ≤ to <116, 116 ≤ to <124, 124 ≤ to <132, 132 ≤ to <140, 140 ≤ to <148, 148 ≤ to <156, 156 ≤, unknown

in the follow-up:

6.3.3. Incidences of adverse drug reactions/adverse events by sex (Table 2.031x, 2.041x, 2.071x, 2.081x)

Analyzed:	Safety analysis population, safety analysis population (patients for whom follow-up survey forms were collected)
Analysis details:	
For adverse drug reactions/adverse events, the proportions will be calculated for each SOC and PT by safety evaluation items and by patients with specific backgrounds and by seriousness (serious/overall). As for the order of output, data will be output in the descending order of the number of subjects by SOC in the total/overall column, in the descending order of the number of subjects by PT, and in the order of PT codes.
 
Adverse events in the safety specifications will be tabulated as necessary.
 
Reasons for use of this drug (Presence or absence of severe lupus nephritis, presence or absence of severe central nervous system lupus) will also be tabulated. *This should be done similarly for events collected as follow up (Table 2.071x).
 
Adverse events will be tabulated by discontinued patients and by prior therapeutic drug. (Table 2.04115~24)
 
Tabulation Tables 2.03101~08 and 2.04101~08 for adverse events and adverse reactions will be summarized into one table to prepare tabulation tables. (Table 2.08101~08, Table 2.08115~24)

Safety Specification:	“Safety Specification ”
Patients with Specific Backgrounds	Age [years], Pregnancy, Renal impairment, Hepatic impairment

6.3.4. Onset status of related AEs by route of administration (Table 9.1, 9.2.1, 9.2.2)

Analyzed:	Safety analysis population
Analysis details:	
For adverse drug reactions, the proportion of each SOC/PT will be tabulated by seriousness (serious/all) by the following items. As for the order of output, data will be output in the descending order of the number of subjects by SOC in the total/overall column, in the descending order of the number of subjects by PT, and in the order of PT codes.

Items:	Route of administration, switching route of administration for intravenous infusion, switching route of administration for subcutaneous injection

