The study will include all patients to whom Benlysta is administered (except patients aged <15 years who start Benlysta administration since approval for paediatric dosage*). In addition, among patients who start the administration after launch, those to whom Benlysta has already administered before the conclusion of the contract and those who has already started administration at diagnosis, because of hospital transfer, etc. will be included as well.

* : Because the study for paediatric patients is separately conducted following approval for paediatric dosage

The [INDICATIONS] of PRECAUTIONS CONCERNING INDICATIONS of Benlysta are as follows (For details, see the latest Package Insert).

< Revised: October 2019 (Version 4), excerpts from the Package Insert >

【INDICATIONS】

Patients with systemic lupus erythematosus (SLE) who inadequately respond to existing treatments

PRECAUTIONS CONCERNING INDICATIONS

1. Administer Benlysta to patients additionally if they have disease activity even if they are treated for SLE appropriately with steroids and immunosuppressants etc. in the past.
2. Use Benlysta in SLE patients who are confirmed positive for autoantibodies, such as anti-nuclear antibody and anti-double stranded DNA (anti-dsDNA) antibody.

3. In clinical studies, the effectiveness and safety of Benlysta have not been investigated in SLE patients with severe lupus nephritis or severe central nervous system (CNS) lupus (See "CLINICAL STUDIES" section).
4. In clinical studies, the effectiveness and safety of Benlysta have not been investigated in combination with other biologics or intravenous cyclophosphamide (See "CLINICAL STUDIES" section).
5. Be well informed about the contents of "CLINICAL STUDIES" section and have good understanding of the effectiveness and safety of Benlysta and select appropriate patients (See "CLINICAL STUDIES" section).

4. Target Sample Size and Rationale

- 1) Target number of patients : 600 (as a safety analysis set)
- 2) Rationale : Benlysta may increase sensitivity to infections due to the mechanism of action. In clinical studies, there were some reports of patients who had a fatal course. Focusing on serious infections, the incidence rates of the serious adverse event (AE) "Infections and Infestations" (SOC) were 5.3% (25/470 patients) and 4.1% (23/556 patients) in the phase III international joint studies [Study BEL113750 (intravenous administration) and Study BEL112341 (subcutaneous administration)], respectively.

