Under the assumption that the incidence rate of the serious infections is 5.3% as a threshold on the basis of the results of the phase III international joint studies, 553 patients are required to monitor the incidence rate in the post-marketing surveillance with estimation accuracy that enables a power for the 5.3% threshold to be $\geq 80\%$ in case where the real risk exists 1.5 times or more of the threshold. It is considered possible to evaluate occurrence of the serious infections in the special DUI (SDUI) having 600 patients as a target sample size.

The incidence rate of ADRs occurring in one patient was 0.2% in the phase III international joint studies. The power to detect an ADR whose incidence rate of 0.2% is 69.9% in at least one patient out of 600 patients.

5. Planned Number of Medical Institutions by Department

All medical institutions where Benlysta is prescribed (except medical institutions that prescribe Benlysta only for patients aged <15 years since approval for paediatric dosage)

6. Study Period

1. Study conduct

Study period : launch date of Benlysta to three months after termination of the observation period in patients eligible for case report form (CRF) collection (period of the follow-up investigation, if conducted) or lifting date of approval conditions, whichever comes later

Observation period :

The observation period per patient will be 52 weeks from the start of Benlysta administration.

For patients who continue administration at the end of the observation period, conduct the two-year follow-up investigation as much as possible, and monitor occurrence of AEs leading to death, serious infections, PML, and MT.

If a patient has withdrawn from /terminated administration of Benlysta, it will be until the withdrawal/termination.

Scheduled enrolment period : launch date of Benlysta to six months after lifting of approval conditions

Patients are eligible for CRF collection when starting Benlysta administration by 31 October, 2018, and CRFs will be collected as required when patients start the administration since 1 November, 2018. Additionally, patients are eligible for enrolment when starting the administration by the acknowledgment of the report at a committee meeting, where the all-case investigation-related conditions for approval are lifted (except patients aged <15 years who start Benlysta administration since approval for paediatric dosage), and enrolment will continue.

2. Study end

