- ii) Number of patients included in the safety analysis set and number of patients included in the effectiveness analysis set, number of patients excluded from analysis and the reason for exclusion

2) Safety-related matters

- i) Occurrence of ADRs/infections (type, severity, and incidence rate of ADRs, etc.)
- ii) Factors that potentially affect safety (occurrence of ADRs and infections by patient characteristics, etc.)
- iii) Occurrence of ADRs of events defined as a priority study matter

3) Effectiveness-related matters

- i) Changes in SELENA SLEDAI score, Lupus Impact Tracker score, PGA score, steroid dose, each laboratory test item, and achievement of Lupus Low Disease Activity State (LLDAS)

2. Analysis methods

Concerning the items associated with safety and effectiveness, etc., the odds ratio and 95% confidence interval will be calculated for the factors that potentially affect them. These will be graphically presented using a forest plot, etc., as appropriate. For comparison of the scores, etc., the mean values and quartile points, etc. for values at the time of measurement and changes from baseline will be calculated.

10. Organizational Structure

See Attachment 1.

11. Name, Address of the Outsourcees, and the Scope of the Outsourced Operations

CCI

12. Scheduled Timing to Be a Milestone for Assessing the Status and Results in the Study or Reporting to the Pharmaceuticals and Medical Devices Agency (PMDA) and Rationale

- At the time of Periodic Safety Reports : consideration will be comprehensively given to the safety and effectiveness information.
- At the time of re-examination application : the final report will be prepared/submitted, based on the results of tabular analysis obtained from the fixed data of all collected CRFs.

13. Additional Measures that Have a Potential to Be Taken Depending to the Study Results and the Decision Criteria for the Start

The Risk Management Plan, including the following, will be reviewed at the timings to be a milestone.

- Regarding the safety specification, including the priority study matters, if the proportion of occurrence, peak occurrence period and risk factors become visible as an ADR caused by Benlysta, the necessity for revising the Package Insert and study materials will be considered as appropriate.
- Including whether or not a new concern in the safety specification is present, the necessity for changes in the content of plan in the study will be considered.

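### Year-1 onset bars use intervals 2, 4 and 8 weeks wide with no scaling or number at risk, so they can suggest a false late peak or mask a moderate early one

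*SAP*

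**What the plan says.** SAP 6.3.2 tabulates time to onset by category for the safety analysis population. It adds bar graphs for adverse events and serious adverse events, and for hypersensitivity, infections, depression and suicidality, and malignancy: "a bar graph will be prepared for each category of time to onset (weeks"). The graphed quantity is described by events and patients. The text does not say whether that is a ratio or two counts.

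The year-1 categories begin "<2, 2 ≤ to <4, 4 ≤ to <8, 8 ≤ to <12", continue in 4-week steps to week 28, and end "28 ≤ to <36, 36 ≤ to <44, 44 ≤ to <52, 52 ≤, unknown". The separate categories for follow-up events are equal 8-week steps from week 52 to week 156, between an under-52 class and an open class.

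The section also plans cumulative percentages, with each patient counted at first occurrence. It names no estimator, number at risk or person-time per interval.

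Protocol section 6 ends a patient's observation at withdrawal or termination of treatment. Protocol section 13 says that if "the proportion of occurrence, peak occurrence period and risk factors become visible as an ADR caused by Benlysta", the need to revise the Package Insert and study materials will be considered.

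**The concern.** A reader looks for a peak by comparing bar heights. When interval width changes from 2 to 4 to 8 weeks, height reflects width as well as risk: at the same weekly risk, an 8-week bar collects about four times the events of a 2-week bar. The largest artefact between neighbouring late bars is at week 28, where width doubles in one step.

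Loss of patients is a second and separate problem. Fewer patients are under observation late in the year, so late events come from a smaller group. This lowers late bars, partly offsetting the width effect, and lowers any cumulative percentage computed over a fixed denominator.

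At stake is the reading of when priority events occur. A flat risk could be described as peaking after week 28, or a moderate excess in the first two weeks could go unnoticed.

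**Working it through.** SAP 6.3.2 states no figure on this point, so there is none to reproduce. The check applies the SAP's own categories to a population in which there is no peak.

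**Inputs**
- N = 600, from Protocol section 4: "Target number of patients : 600 (as a safety analysis set").
- 5.3%, from Protocol section 4: "the incidence rate of the serious infections is 5.3% as a threshold" (25/470 = 5.3%). It is taken here as the proportion with a first event by week 52 when everyone is observed; that reading is an assumption.
- Discontinuation by week 52: not given in the documents. Assumed 0% to 40%, at a constant rate and unrelated to event risk.

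**Formulas**
- Event hazard: h = -ln(1 - 0.053)/52 = 0.00105 per week, or 5.46 per 100 patient-years.
- Discontinuation hazard: g = -ln(1 - d)/52, where d is the proportion discontinuing.
- Expected first events between weeks a and b: N × h/(h+g) × [exp(-(h+g)a) - exp(-(h+g)b)].

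Worked case, no discontinuation, weeks 28-36: 600 × [exp(-0.02932) - exp(-0.03770)] = 600 × 0.00810 = 4.86.

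**Results under a constant hazard**

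| Discontinued by week 52 | Events, weeks 0-2 | Weeks 24-28 | Weeks 28-36 | 28-36 vs 24-28 | 28-36 vs 0-2 | Crude cumulative % at week 52 |
|---|---|---|---|---|---|---|
| 0% | 1.26 | 2.45 | 4.86 | 1.98 | 3.86 | 5.3 |
| 10% | 1.25 | 2.32 | 4.56 | 1.97 | 3.65 | 5.0 |
| 20% | 1.25 | 2.19 | 4.24 | 1.94 | 3.39 | 4.8 |
| 30% | 1.25 | 2.05 | 3.90 | 1.90 | 3.12 | 4.5 |
| 40% | 1.24 | 1.89 | 3.55 | 1.88 | 2.86 | 4.2 |

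**Masking of an early excess.** If the rate in weeks 0-2 is three times the later rate, the first bar roughly triples. The 28-36 bar is then 3.86/3 = 1.29 times the first bar with no discontinuation, 3.39/3 = 1.13 times at 20%, and 2.86/3 = 0.95 times at 40%. A threefold early rate gives the shorter bar in the first two cases and about the same bar in the third.

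**Commoner events.** If 30% have an event by week 52 (an assumption), the 28-36 bar is 1.92 to 1.81 times the 24-28 bar and 3.24 to 2.39 times the first bar, over the same discontinuation range. The direction is the same and the size somewhat smaller.

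**Scaling for width alone.** Events per week in weeks 44-52, relative to weeks 0-2, would be 0.95, 0.87, 0.78, 0.69 and 0.60 at 0%, 10%, 20%, 30% and 40% discontinuation, although the hazard is constant. The number at risk is therefore needed as well.

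**After the change.** First events divided by patient-time in the interval give 5.46 per 100 patient-years in every interval at every discontinuation level. One minus Kaplan-Meier gives 5.3% at week 52 throughout.

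**The case against.** The interval limits are printed, so a careful reader can rescale by width. The six intervals from week 4 to week 28 are equal and directly comparable, and an early rate more than about three to four times the later one would still stand out. This stands: the display can mislead, but a reader would go too far in inferring that it cannot show a peak at all.

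A reader might also infer that unequal widths bias the cumulative percentages. They do not: at each interval limit the cumulative figure is unaffected by width. Only the shrinking number at risk matters there, and only if the denominator is the whole safety set. That is the natural reading, but it is not written. The table shells are not among the documents and SAP 5.4 and 6.6 are redacted, so a number at risk given there cannot be excluded.

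Other outputs help in part. SAP 6.3.7 times serious hypersensitivity over the first six doses. SAP 6.2.6 gives time on drug in the same year-1 categories, with Kaplan-Meier curves. SAP 6.3.8 gives person-year rates. But 6.3.7 covers one topic, 6.2.6 is not linked to onset, and 6.3.8 gives a single rate per event, not one per interval.

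A reader might see a further error in the rule that an unknown onset date "in the same case shall be counted preferentially". It is defensible: an undated event may have come first, so first onset is then truly unknown.

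Finally, Protocol section 13 says only that revision will be considered. A peak is not an automatic trigger.

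**Conclusion.** The point holds for the year-1 bars. Read as written, SAP 6.3.2 gives a near-doubling at week 28 (1.98-fold to 1.88-fold) when the risk is flat. This hardly depends on the discontinuation assumption. The contrast with the first two weeks, 3.9-fold to 2.9-fold, depends on it more. A moderate early excess, up to about threefold, can be masked.

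The cumulative percentage has a smaller and separate problem: a true 5.3% would read as 5.3% to 4.2%, a shortfall of 0 to 1.1 points, if the denominator is the whole safety set. The year-2 and year-3 follow-up intervals are of equal width, so only the at-risk point applies to them.

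These sizes rest on a constant hazard, 600 patients, 5.3% by week 52, and an assumed 0% to 40% discontinuation unrelated to event risk. This is a cheap improvement to a descriptive display; the data collected are not in question.

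**What to change.** In SAP 6.3.2, for each onset interval, add the number of patients at risk at its start and the first events per 100 patient-years within it. In the year-1 figures, plot that rate in place of, or beside, the raw bars. Beside the crude cumulative percentage, add 1 minus Kaplan-Meier for first onset, censored at the end of observation, and state the denominator of the crude figure. For the follow-up tables, add the number at risk and the Kaplan-Meier estimate. Leave the rule on unknown dates as it is; a display using the earliest known date is at most a sensitivity check.

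The SAP already uses patient-years (5.5) and Kaplan-Meier methods (6.2.6, 6.4.14), and no new data are needed. The cost is extra programming and a written definition of the risk period. That definition needs care: SAP 4.5 replaces some end dates with deemed durations of 168 or 364 days, and SAP 4.15 counts the 52-week event window from first dose, not by time on drug. With about 1 to 5 expected serious infections per interval, the rates will be imprecise, so event counts should be shown beside them. If the tables scheduled in Protocol section 6 for July 2025 have already been run, this can be a supplementary output to the final report.
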